## Study Design

This is a Phase III, open-label, active-controlled, parallel-group, multi-center study to compare the efficacy (demonstration of non-inferiority) and safety of GSK1278863 administered for 52 weeks versus epoetin beta pegol in approximately 270 Japanese ND subjects with renal anemia. This study also includes an open-label, uncontrolled part to evaluate the efficacy and safety of GSK1278863 in approximately 50 Japanese PD subjects. The study consists of the following 2 cohorts of different patient populations:

	Patient population	Presence or absence of ESA therapy (Hgb in subjects)	Treatment group	Target number of subjects (randomized/enrolled)
Cohort 1	ND patient	ESA non-user (Hgb 8.0-<11.0 g/dL) ESA user (Hgb 9.0-13.0 g/dL)	GSK1278863 group	135 subjects*
			Epoetin beta pegol group	135 subjects*
Cohort 2	PD patient	ESA non-user (Hgb 8.0-<11.0 g/dL) ESA user (Hgb 9.0-13.0 g/dL)	GSK1278863 group	50 subjects

[figure not shown]
\*: At least 50 ESA users and at least 50 ESA non-users will be randomized to Cohort 1.

ESA: erythropoiesis-stimulating agent

In Cohort 1, 270 eligible ND subjects will be stratified by the current ESA therapy and baseline Hgb (ESA non-users: ≤9.5 g/dL, >9.5 g/dL, ESA users: <11.0 g/dL, ≥11.0 g/dL) and then randomized in a 1:1 ratio to GSK1278863 or epoetin beta pegol group (135 subjects per group).

In Cohort 2, 50 eligible PD subjects will be included in the GSK1278863 group.

This study consists of a 4-week screening phase, a 52-week treatment phase [including the primary efficacy evaluation period (Weeks 40 to 52)], and a 4-week follow-up phase following the treatment phase. The study design is shown below.

Week -4

Day 1

Week 40

Week 52

Week 56

## **Method of Administration of Study Medication in Each Treatment Group**

In each treatment group, study medication will be administered as follows:

- GSK1278863 group (ND and PD subjects): Treatment with GSK1278863 will be started at a dose of 4 mg once daily on Day 1. From Week 4 onwards, dose adjustments will be made within the dose range of 1-24 mg every 4 weeks according to the prespecified dose adjustment algorithm to achieve and/or maintain Hgb within the target range (11.0-13.0 g/dL).
- Epoetin beta pegol group (ND subjects):
  - ESA non-users: Subcutaneous treatment with epoetin beta pegol will be started at a dose of 25 µg once every 2 weeks on Day 1. Subsequently, dose adjustments will be made within the dose range of 25-150 µg every 4 weeks according to the prespecified initial dose adjustment criteria to achieve the lower limit of the Hgb target (11.0 g/dL). Once Hgb increases to 11.0 g/dL or more, dose adjustments will be made according to the prespecified dose adjustment algorithm. After it is confirmed that all of the criteria for dosing interval change are met, dosing frequency will be changed to once every 4 weeks, and dose adjustments will be made within the dose range of 25-250 µg every 4 weeks according to the prespecified dose adjustment algorithm to achieve and/or maintain Hgb within the target Hgb range (11.0-13.0 g/dL).
  - ESA users: Prior ESA therapy will be replaced with subcutaneous treatment with epoetin beta pegol at the equivalent dose once every 4 weeks according to prespecified dose conversion. Subsequently, dose adjustments will be made within the dose range of 25-250 µg every 4 weeks according to the prespecified dose adjustment algorithm to achieve and/or maintain Hgb within the target range (11.0-13.0 g/dL).

## **Analysis**

Assuming a non-inferiority margin of -1.0 g/dL, a treatment difference of 0.0 g/dL, and a standard deviation of 1.5 g/dL for mean Hgb during in the primary efficacy evaluation period in ND subjects, two-sample t-test has at least 99% power at a two-sided significance level of 5% with a sample size of 100 subjects per group. Assuming a dropout rate of approximately 25%, 135 subjects will be randomized to each group. For PD subjects, the sample size is based on the feasibility. Assuming a sample size of 38 subjects and a standard deviation of 1.5 g/dL, the half the width of the 95% CI for mean Hgb during in the primary efficacy evaluation period is 0.493 g/dL.

The primary endpoint, which is the mean Hgb during the primary efficacy evaluation period, will be analyzed to demonstrate the non-inferiority of GSK1278863 to epoetin beta pegol in ND subjects. A mixed model for repeated measurements (MMRM) will be used to estimate the mean Hgb during the primary efficacy evaluation period and its 95% CI by treatment groups. As a preliminary assessment, it will be confirmed if the lower and upper limit of 95% CI for mean Hgb in GSK1278863 group would lie fully within target range (11.0-13.0 g/dL) In addition, the point estimate and 95% CI for the treatment difference (GSK1278863-epoetin beta pegol) in mean Hgb during the primary efficacy evaluation period will be estimated. Non-inferiority will be established if the lower limit of the 95% CI is greater than -1.0 g/dL. Even if the 95% CI for the difference is completely negative (i.e.

lies fully within the range -0.75 to <0 g/dL) non-inferiority would still be concluded on condition that the mean Hgb estimate in the GSK1278863 group is within the target range.

The primary efficacy population will be the ITT Population, and the analysis will be repeated in the mITT and PP Population to evaluate the robustness of the conclusion. The subgroup analysis by the current ESA therapy (presence or absence) will also be conducted. Further details of sensitivity analyses will be provided in the Reporting and Analysis Plan (RAP).

The principal secondary endpoint, which is the proportion of subjects whose mean Hgb during the primary efficacy evaluation period is within the target range will be analyzed to demonstrate the superiority of GSK1278863 to epoetin beta pegol in ND subjects.

In the mITT Population, a logistic regression model including treatment group, baseline Hgb, and the current ESA therapy (presence or absence) as covariates will be used to estimate the point estimate and 95% CI for the odds ratio (GSK1278863/epoetin beta pegol). This analysis will be performed to demonstrate the superiority at a two-sided significance level of 5%, conditional on the primary endpoint achieving noninferiority. Superiority will be established if the lower limit of the 95% CI for the odds ratio is greater than 1.0.

## 2. INTRODUCTION

GSK1278863 is a hypoxia-inducible factor (HIF)-prolyl hydroxylase inhibitor (PHI) that stimulates erythropoiesis in the same manner as innate response to hypoxia and is currently being developed as a new treatment for renal anemia.

### 2.1. Study Rationale

This is a Phase III study to evaluate the efficacy and safety of GSK1278863 in Japanese non-dialysis (ND) and peritoneal dialysis (PD) subjects with renal anemia. The primary objective is to demonstrate non-inferiority of GSK1278863 to epoetin beta pegol based on hemoglobin (Hgb) in the ND patient population included in this study. Study results will be used as pivotal study data for an NDA submitted for GSK1278863 for the treatment of renal anemia in Japan.

### 2.2. Background

Renal anemia is diagnosed in many patients with CKD, and the prevalence of renal anemia increases with progression of CKD [Akizawa, 2011]. Causes of anemia in CKD patients include absolute or relative deficiency of erythropoietin (EPO), shortened erythrocyte survival, and reduced iron availability. Anemia is further exacerbated by chronic blood loss associated with hemodialysis procedure, infection, and functional hemolysis [Japanese Society for Dialysis Therapy, 2008].

GSK1278863 is a hypoxia-inducible factor-prolyl hydroxylase inhibitor that is currently being developed as a treatment for renal anemia. Data in Japanese patients have been collected from a Japanese Phase II 4-week treatment study in Japanese hemodialysis (HD) subjects (PHI116099: 97 Japanese subjects), an international multi-center Phase II 24-week treatment study in HD subjects (PHI113633: including 24 Japanese subjects), and an international multi-center Phase II 24-week treatment study in ND subjects (PHI113747: including 42 Japanese subjects). In these clinical studies, GSK1278863 increased endogenous EPO, reduced hepcidin, and increased Hgb in HD and ND subjects including Japanese subjects. In addition, GSK1278863 increased Hgb at lower blood EPO concentrations than existing erythropoiesis-stimulating agents (ESAs).

Data from completed clinical and clinical pharmacology studies and the preclinical data safety package are provided in the Development Core Safety Information found in the current GSK1278863 Investigator Brochure (IB). A benefit: risk assessment, including risk mitigation strategies, is outlined in Section 4.6.

## 3. OBJECTIVES AND ENDPOINTS

Objective	Endpoint
Primary (efficacy)	

 
To demonstrate non-inferiority of GSK1278863 to epoetin beta pegol based on hemoglobin (Hgb) in ND subjects
 
	
 
Mean Hgb during the primary efficacy evaluation period (Weeks 40 to 52)
 

Principal secondary (efficacy)	

 
To demonstrate superiority of
 
	
 
Number (%) of subjects with mean Hgb in the
 

Objective	Endpoint
GSK1278863 to epoetin beta pegol in terms of achievement/maintenance of target Hgb in ND subjects	target range (11.0-13.0 g/dL) during the primary efficacy evaluation period (Weeks 40 to 52)
Other secondary (efficacy, PK)	

 
To evaluate the appropriateness of the starting dose of GSK1278863 in ND subjects using epoetin beta pegol as control
 
To evaluate the appropriateness of the starting dose of GSK1278863 in PD subjects
 
	
 
Change in Hgb from baseline to Week 4 (Hgb increase rate)
 
Number (%) of subjects by Hgb change from baseline category to Week 4
 

 
To evaluate dose adjustments of GSK1278863 in ND subjects using epoetin beta pegol as control
 
To evaluate dose adjustments of GSK1278863 in PD subjects
 
	
 
Distribution of the dose level
 
Duration of treatment interruption due to Hgb >13 g/dL
 
Frequency of dose adjustments
 


 
To evaluate the overall Hgb control by GSK1278863 in ND subjects using epoetin beta pegol as control
 
To evaluate the overall Hgb control by GSK1278863 in PD subjects
 
	
 
Hgb at each assessment time point and change in Hgb from baseline to each assessment time point
 
Number (%) of subjects with Hgb within the target range (11.0-13.0 g/dL) at each assessment time point
 
Proportion (%) of time with Hgb within the target range (11.0-13.0 g/dL) in the primary efficacy evaluation period (Weeks 40 to 52)
 
Time (number of days) to the lower Hgb target (11.0 g/dL)
 
Number (%) of subjects who have an Hgb level of less than 7.5 g/dL
 
Number (%) of subjects who have an Hgb increase of more than 2 g/dL over any 4 weeks before Week 52
 
Number (%) of subjects who achieve an Hgb level of more than 13.0 g/dL and number of episodes
 

 
To compare the effect of GSK1278863 versus epoetin beta pegol on iron use in ND subjects
 
To evaluate the effect of GSK1278863 on iron use in PD subjects
 
	
 
Dose of oral iron in the study period and the primary efficacy evaluation period (Weeks 40 to 52)
 
Number (%) of subjects who use oral iron during the study period and the primary efficacy evaluation period (Weeks 40 to 52)
 

• To compare the effect of GSK1278863	• Change in ferritin from baseline

Objective	Endpoint
versus epoetin beta pegol on iron metabolism in ND subjects	
 
Change in transferrin saturation (TSAT) from baseline
 

 
To evaluate the effect of GSK1278863 on iron metabolism in PD subjects
 
To evaluate the PK of GSK1278863
 
	
 
Changes in hepcidin, serum iron, and total iron binding capacity (TIBC) from baseline
 
AUC and Cmax of plasma GSK1278863
 

Exploratory (efficacy)	

 
To compare the effect of GSK1278863 versus epoetin beta pegol on progression of CKD in ND subjects
 
	
 
Estimated glomerular filtration rate (eGFR) and change from baseline
 
Serum creatinine and change from baseline
 
Urine creatinine and urine albumin, and changes from baseline
 
Urine albumin/creatinine ratio and change from baseline
 

Patient reported outcome	

 
To compare the effect of GSK1278863 versus epoetin beta pegol on health-related QoL (HR-QoL) in ND subjects
 
To evaluate the effect of GSK1278863 on H-RQoL in PD subjects
 
	
SF-36
 
 
Changes in SF-36 HR-QoL scores (PCS, MCS, and 8 subscales) from baseline
 
 
EuroQol Health Utility Index (EQ-5D-5L)
 
 
Change in EQ-5D-5L score from baseline
 
Change in EQ-5D-5L Visual Analog Scale (VAS) from baseline
 

Safety	

 
To evaluate the safety and tolerability of GSK1278863 in ND and PD subjects
 
	
 
Incidence and severity of AEs and SAEs, including AEs of special interest
 
Reasons for discontinuation of study medication
 
Laboratory tests, ECG, vital signs, and ophthalmology assessments
 

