	
(11.0 g/dL)
 
 
Number (%) of subjects who have an Hgb level of less than 7.5 g/dL
 
Number (%) of subjects who have an Hgb increase of more than 2 g/dL over any 4 weeks
 
Number (%) of subjects who have an Hgb level of more than 13.0 g/dL and number of episodes
 

 
To evaluate the effect on iron use of GSK1278863 in ND subjects using epoetin beta pegol as control
 
To evaluate effect on iron use of GSK1278863 in PD subjects
 
	
 
Dose of oral iron during the study period and the primary efficacy evaluation period (Weeks 40 to 52)
 
Number (%) of subjects who use oral iron during the study period and the primary efficacy evaluation period (Weeks 40 to 52)
 

 
To evaluate the effect on iron metabolism of GSK1278863 in ND subjects using epoetin beta pegol as control
 
To evaluate the effect on iron metabolism of GSK1278863 in PD subjects
 
	
 
Change from baseline in ferritin
 
Change from baseline in transferrin saturation (TSAT)
 
Changes from baseline in hepcidin, serum iron, and total iron binding capacity (TIBC)
 

 
To evaluate the PK of GSK1278863
 
	
 
AUC and Cmax of plasma GSK1278863
 

Exploratory (efficacy)	

 
To evaluate the effect on progression of Chronic Kidney Disease (CKD) of GSK1278863 in ND subjects using epoetin beta pegol as control
 
	
 
Estimated glomerular filtration rate (eGFR) and change from baseline
 
Serum creatinine and change from baseline
 
Urine creatinine and urine albumin, and changes from baseline
 
Urine albumin/creatinine ratio and change from baseline
 

Patient reported outcome	

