### **Treatment phase**

Subjects who meet all of the eligibility criteria at the start of the treatment phase (Day 1) will be enrolled in the study. Study medication (either GSK1278863 or epoetin beta pegol group) will be administered for 52 weeks according to randomization in Cohort 1 and GSK1278863 will be administered in Cohort 2 for 52 weeks. For ESA users, prior ESA will be replaced with study medication on Day 1. GSK1278863 will be orally administered once daily, and epoetin beta pegol will be subcutaneously administered once every 2 or 4 weeks. In both groups, dose adjustments for study medication during the treatment phase will be made according to the administration schedule specified in Section 6.4. to achieve and/or maintain Hgb within the target range (11.0-13.0 g/dL). In addition, supplemental iron therapy will be administered according to the standard initiation criteria as described in Section 6.12.. It should be noted that intravenous iron or dose change for oral iron will not be allowed from Day 1 to Week 4.

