## **6.12. Supplemental Iron Therapy**

Supplemental iron therapy will be administered according to the Guidelines for Renal Anemia [The Japanese Society for Dialysis Therapy, 2008] if ferritin is  $\leq 100$  ng/mL and TSAT is  $\leq 20\%$ . The investigator (or subinvestigator) can choose the route of administration and dose of prescription iron.

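### The iron-use objective is measured by oral iron alone, although intravenous iron is permitted after Week 4, so iron use can be understated or falsely differ between arms

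*Protocol*

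**What the plan says.** Section 3 of the protocol states the objective for Cohort 1 as "To compare the effect of GSK1278863 versus epoetin beta pegol on iron use in ND subjects" and for Cohort 2 as "To evaluate the effect of GSK1278863 on iron use in PD subjects". Neither is limited by route. Two endpoints serve these objectives: "Dose of oral iron in the study period and the primary efficacy evaluation period (Weeks 40 to 52") and "Number (%) of subjects who use oral iron during the study period and the primary efficacy evaluation period (Weeks 40 to 52"). The synopsis restricts them in the same way, for example "Dose of oral iron during the study period and the primary efficacy evaluation period (Weeks 40 to 52"). No endpoint under the objective mentions intravenous iron.

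The treatment rules are wider than the endpoints. Section 4.2 bars IV iron during screening and, in the treatment phase, adds that "intravenous iron or dose change for oral iron will not be allowed from Day 1 to Week 4". Exclusion criterion 12 in Section 5.2 covers the same two periods and no others. From then on, Section 6.12 triggers supplemental iron when ferritin and TSAT are both low and says: "The investigator (or subinvestigator) can choose the route of administration and dose of prescription iron". Section 6.11.2 prohibits only strong CYP2C8 inhibitors and inducers, and Section 6.11.1 permits whatever is not prohibited. Section 6.11 requires dose, route and frequency to be recorded for iron.

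**The concern.** The endpoints cover a narrower quantity than the objective. Iron given intravenously is iron use in the sense of the objective, but it enters neither endpoint. Because no other endpoint serves the objective, absence of oral iron would be read as absence of iron.

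The trial is open-label, so whoever chooses the route knows the treatment arm. The argument in Section 4.4 that the open label is harmless rests on Hgb being an objective measure and on algorithm-driven dosing of study medication. Neither reaches the choice of iron route. A between-arm contrast in oral iron could therefore reflect route preference rather than iron use. Section 2.1 describes the results as pivotal data for a Japanese application, so a statement about iron use drawn from these endpoints should measure iron use.

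**Working it through.** The plan gives no iron-use figure to reproduce. The check is a comparison of definitions, followed by an illustration on stated assumptions.

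**Step 1. When IV iron can be given.** It is barred in screening and from Day 1 to Week 4 (Sections 4.2 and 5.2). Of the 52 treatment weeks, 52 − 4 = 48 remain in which it is permitted, including all of Weeks 40 to 52, the window that the endpoints single out.

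**Step 2. How each kind of subject is scored.**

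| Iron received on study | Study period | Weeks 40 to 52 |
|---|---|---|
| Oral only, throughout | User, full dose | User, full dose |
| IV only | Non-user, dose 0 | Non-user, dose 0 |
| Oral, then IV only from before Week 40 | User; oral dose counted, IV dose not | Non-user, dose 0 |
| Oral and IV together in the window | User; IV dose not counted | User; IV dose not counted |
| None | Non-user, dose 0 | Non-user, dose 0 |

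The second row, and the third row in the later window, cannot be told apart from the last row.

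**Step 3. Possible size.** Let u be the true proportion using any iron in an arm, and s the share of those users who receive IV iron only in the window concerned. The oral-only endpoint then reads

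oral-user rate = u × (1 − s).

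With the same u in both arms, s = 0 in one arm and s > 0 in the other, the false difference is u − u(1 − s) = u × s. The protocol supplies neither u nor s, so both are assumptions.

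| Assumed u, both arms | Assumed s in one arm | Reading, s = 0 arm | Reading, other arm | False difference (points) |
|---|---|---|---|---|
| 30% | 10% | 30% | 27% | 3 |
| 30% | 25% | 30% | 22.5% | 7.5 |
| 40% | 10% | 40% | 36% | 4 |
| 40% | 25% | 40% | 30% | 10 |
| 50% | 10% | 50% | 45% | 5 |
| 50% | 25% | 50% | 37.5% | 12.5 |

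**Step 4. Equal IV share in both arms.** There is then no false difference, but each arm is understated. With u = 40%, both read 0.40 × 0.90 = 36% at s = 10%, or 0.40 × 0.75 = 30% at s = 25%.

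**The case against.** The best case for leaving the text alone is that little depends on it. Section 9.3.3 treats the other secondary endpoints as complementary or exploratory. Section 9.4.3 lists those that receive a treatment difference with a confidence interval, and iron use is not among them; it is summarized by group. Ferritin, TSAT, hepcidin, serum iron and TIBC do receive such estimates and do not depend on the route of supplementation. The endpoints are openly labelled as oral iron, and route is recorded, so an analysis plan could add an IV table. All of this stands and limits the weight of the point. It does not close the gap, because the oral-only wording is fixed in the protocol in two places and would remain the formal measure of the objective.

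Three stronger readings are tempting, and the documents do not support them:

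- A reader might infer that anyone moved to IV iron is scored as using no iron. One of the two windows is the whole study period, and a subject who took oral iron on study before the switch remains a user there, with the oral dose counted.
- A reader might infer that route choice must differ by arm because one arm takes tablets at home and the other is injected at the site. Table 13 gives both arms 4-weekly visits, and maintenance epoetin beta pegol is also 4-weekly (Section 6.4.2.3). The extra 2-weekly visits concern control-arm ESA non-users before their interval change. A difference in route is possible in an open-label trial, but nothing in the protocol shows it. Nor does it say that a move to IV iron means greater iron need.
- A reader might put the loss at 10 points for every 10% of an arm given IV instead of oral iron (0.10 × 135 = 13.5 subjects). That only restates the assumption, with all randomized subjects as the base. For 10% of iron users, the table above gives 3 to 5 points. In Weeks 40 to 52 the base is also smaller: Section 4.3 expects 202 completers, about 101 per arm.

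**Conclusion.** The point holds as a mismatch between objective and endpoints. The objective is route-neutral, IV iron is permitted after Week 4 at the investigator's choice, and the only two endpoints leave it out. Subjects given only IV iron are scored as non-users with zero dose in both windows. Those moved to IV before Week 40 are scored so in Weeks 40 to 52.

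The false difference is 3 to 12.5 percentage points if true use is 30% to 50% in both arms and 10% to 25% of users in one arm, and none in the other, receive IV iron only. It is zero if the IV share is equal, and then only understatement remains. These are assumed values and not estimates for this trial. The direction is open, since either arm could have the larger IV share.

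The consequence is confined to other secondary endpoints that are summarized descriptively. The primary non-inferiority analysis and the principal secondary analysis of target-range Hgb are unaffected. The change is worth making because it is cheap, not because a main conclusion is at risk.

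**What to change.** In the synopsis and Section 3, define the user endpoint as the number (%) of subjects using any supplemental iron, oral or intravenous. Show oral users, IV users, oral dose and IV dose separately beneath it. Do this for the study period and for Weeks 40 to 52.

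State whether iron-containing antihyperphosphatemic agents count. Section 6.11.1 allows them to be started from Week 4, so a definition based on any iron is ambiguous until this is settled.

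The cost is endpoint wording and some added table rows. Iron dose, route and frequency are already recorded under Section 6.11, so no new data are needed, and no rule on giving iron changes.
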